7.1 Effectiveness Endpoints

The primary and secondary effectiveness endpoints will be summarized using the modified FAS population with missing data replaced as described in Section 7.4.1; for sensitivity purposes, these analyses will also be performed on the modified FAS with observed data and on the PPS. [REDACTED]

Statistical tests will be one-sided binomial tests at error level 2.5% for the responder rates in general. Adequate [REDACTED] statistics will be provided for each variable for the pooled data and by realized treatment group. The supportive exploratory analyses for the primary effectiveness endpoint will also be performed on the observed cases in the FAS. Metric variables will be summarized by number of observations (Nobs), number of missing values (nmiss), mean, standard deviation, median, minimum, Q1, Q3 and maximum. Categorical variables will be summarized by number and rate of events per category where the denominator will be chosen according to the adequate analysis population. Ordered categorical data may be summarized by metric and categorical statistics. All variables will be analyzed as absolute data and as change from baseline, as applicable.

Summary statistics for all visits and changes from baseline for all post-baseline visits will be displayed for each effectiveness endpoint for each treatment group and the pooled data.

If not otherwise specified, confidence intervals in the following refer to the two-sided 95% Wilson score confidence intervals.

All data captured in the electronic Case Report Form (eCRF) will be listed.

P-values will be reported to four decimal places (e.g., $p=0.0375$). P-values below 0.0001 will be presented as ' <0.0001 '.

Mean, median, and standard deviation will be reported to one decimal place more than the data were collected; for derived data, an adequate number of decimal places will be chosen. Percentages will be calculated using the denominator of all subjects in a specified population or treatment group. The denominator will be specified in a footnote to the tables for clarification if necessary. Percentages will be reported to one decimal place.

7.1.1 Primary Effectiveness Endpoint(s)

The primary effectiveness endpoint is the proportion of responders (responder rate) defined as subjects with ≥ 1 -point improvement on the MAS 'Décolleté Wrinkles – At Rest' from baseline to 16 weeks after last treatment as assessed [REDACTED].

The primary analysis will be based on a one-sided binomial test at the one-sided type I error level of $\alpha = 0.025$ for the pooled data from both treatments against the null-hypothesis that the response rate (R) is $\leq 50\%$:

$$H_0 : R \leq 50\%$$

$$H_1 : R > 50\%.$$

H_0 is rejected if the resulting one-sided p-value is <0.025 and the observed proportion of responders is >0.5 .

As further supportive explorative analyses, the effectiveness for the different time points of treatments with a 16 weeks post-treatment period in both treatment groups will be analyzed as for the primary endpoint:

- Proportion of responders (response rate) defined as subjects with ≥ 1 -point improvement on the 'MAS Décolleté Wrinkles – At Rest' from last treatment application to 16 weeks after last treatment as assessed [REDACTED].
- Proportion of responders (response rate) defined as subjects with ≥ 1 -point improvement on the MAS 'Décolleté Wrinkles – At Rest' from last treatment application to 16 weeks after last treatment as assessed [REDACTED].
- Proportion of responders (response rate) defined as subjects with ≥ 1 -point improvement on the MAS 'Décolleté Wrinkles – At Rest' from baseline to 16 weeks after first treatment as assessed [REDACTED].

In addition, two-sided 95% Wilson score confidence intervals for response rates will be provided overall, and for each treatment group in the supportive analyses. A similar SAS code as given above will be used.

The primary effectiveness analyses will be based on the modified FAS with missing data replaced by a multiple imputation approach for each realized treatment group.

Sensitivity analyses of the primary endpoint will be provided based on observed cases only in the modified FAS and on the observed cases in the PPS. The supportive explorative analyses will be performed on the observed cases in the modified FAS as well as on observed cases in the FAS. For analysis based on observed data, SAS code similar to the following will be used:

```
proc freq data = dataset order = freq;  
  tables response / binomial (level="1" wilson p=.5) cl alpha=.05;  
run;
```

, assuming the response is coded with '1' and no response is coded with '0'.

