12.1 Determination of Sample Size

The primary effectiveness endpoint is the proportion of subjects with at least 1 point (≥ 1 point) improvement on the MAS Décolleté Wrinkles-At Rest scale at 16 weeks after last treatment compared to baseline (Day 1)

. By use of a one-sided binomial test, it will be tested at an error level of 2.5% whether the response rate is significantly larger than 50%. It is aimed to ensure a power of 90%. The binomial test is applied to the pooled data from both treatment groups.

To account for up to 10% drop-outs and potential exclusions from the FAS, a total of 112 subjects need to be enrolled in this study, i.e., 56 subjects need to be randomized to each treatment group.

Per definition, the SES will be at least as large as the FAS. Thus, according to the above outlined assumptions, at least 100 subjects will be available for safety analyses. This sample size is sufficient to observe, with a probability of 80%, at least one adverse event with actual event probability of 1.6%.

With regard to safety analyses, it should be considered that the RADIESSE[®] in its original un-diluted form is marketed since 2003. Since then, over 5 million units had been sold and used in a variety of subject populations. In this period, the majority of reported AEs were common expected injection site reactions that were mild in nature and resolved over time.

Consequently, the sample size for this study was primarily determined to ensure an adequate power for the primary effectiveness analysis, however, still providing a good probability of risk detection.

Calculations to determine the required sample size were performed using the software nQuery Version 8.1.2.0, Statistical Solutions Ltd. 2017, and validated by double programming with proc power on SAS 9.4, SAS Institute Inc., Cary, NC, USA, 2016.

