4 DETERMINATION OF SAMPLE SIZE

The primary effectiveness endpoint is the proportion of subjects with at least 1 point (≥ 1 point) improvement on the MAS Décolleté Wrinkles – At Rest scale at 16 weeks after last treatment compared to baseline (Day 1). [REDACTED]. By use of a one-sided binomial test, it will be tested at an error level of 2.5% whether the response rate is significantly larger than 50%. It is aimed to ensure a power of 90%. The binomial test is applied to the pooled data from both treatment groups. [REDACTED]

Per definition, the safety evaluation set (SES) will be at least as large as the FAS. Thus, according to the above outlined assumptions, at least 100 subjects are planned to be available for safety analyses. This sample size is sufficient to observe, with a probability of 80%, at least one adverse event with actual event probability of 1.6%.

With regard to safety analyses, it should be considered that the RADIÉSSE® in its original undiluted form is marketed since 2003. Since then, over 5 million units had been sold and used in a variety of subject populations. In this period, the majority of reported AEs were common expected injection site reactions that were mild in nature and resolved over time. [REDACTED]

[REDACTED] The large extent of the exposure to the undiluted RADIÉSSE® worldwide versus the relatively small number of complications led to the conclusion that its safety has already been established to a sufficient degree. As it is not expected that dilution of RADIÉSSE® Volume Advantage 1.5 mL Injectable Implant with saline will cause more AEs, it is assumed the safety can be transferred to the IMD.

Consequently, the sample size for this study was primarily determined to ensure an adequate power for the primary effectiveness analysis, however, still providing a good probability of risk detection.

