7.4.1 Discontinuations and Missing Data

Multiple imputation (MI)

Missing post-baseline data for the primary endpoint will be replaced by multiple imputation. Multiple imputations will only be performed for subjects with a missing MAS ‘Décolleté Wrinkles – At Rest’ score at 16 weeks after last treatment who did not discontinue before 16 weeks after last treatment due to lack of effectiveness. Subjects who will discontinue due to the reason given above will be treated as non-responders.

All further specifications for MI are based on the assumption that the MAS ‘Décolleté Wrinkles – At Rest’ assessment at 16 weeks after last treatment is missing at random, i.e.; being missing will not depend on the MAS at 16 weeks after last treatment itself but will only depend on the factors in the imputation model.

[figure not shown]

[figure not shown]
Last observation carried forward (LOCF)

For secondary effectiveness endpoints, missing values will be replaced by the last available value before 16 weeks after last treatment.

Observed cases (OC)

For the OC method, no missing value imputations will be conducted. All data will be analyzed as observed. This method will be used [REDACTED] to assess the sensitivity of the MI and the LOCF method for primary and secondary effectiveness endpoints.

7.4.2 *Interim Analyses*

Not applicable.

7.4.3 *Data Monitoring Committee*

[figure not shown]
Not applicable.

7.4.4 *Multiple Comparisons/Multiplicity*

[REDACTED] the type one error rate has not to be adjusted.

7.4.5 *Examination of Subgroups*

[figure not shown]

The supportive exploratory analyses for the primary effectiveness endpoint will also be performed for the observed cases in the FAS (i.e. on randomized treatment groups).

A further subgroup analysis for the following safety endpoints will be presented for the subgroup of subjects that had three injections with a cannula:

- Adverse events: Incidences of TEAEs, non-serious TEAEs and serious TEAEs will be provided by SOC and PT. Incidences of TEAEs will be provided overall and by worst intensity, by worst outcome, and by treatment area affected (yes/no). Treatment-related TEAEs will be presented by injection cycle.

[figure not shown]

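### Does SAP 7.1.1 need to say whether the observed-case binomial test is exact or asymptotic?

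*SAP*

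**What the plan says.** SAP 7.1 sets a general rule: "Statistical tests will be one-sided binomial tests at error level 2.5% for the responder rates in general". SAP 7.1.1 repeats it for the primary endpoint ("The primary analysis will be based on a one-sided binomial test at the one-sided type I error level of" 0.025, pooled groups), and states that the null hypothesis "is rejected if the resulting one-sided p-value is <0.025 and the observed proportion of responders is >0.5". Protocol 12.1 and 12.4.1.1 use the same name for the test. The visible text nowhere says exact, asymptotic or continuity-corrected.

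For the observed cases SAP 7.1.1 goes further and shows a program, introduced by "For analysis based on observed data, SAS code similar to the following will be used". It is a complete PROC FREQ step whose working line is "tables response / binomial (level='1' wilson p=.5) cl alpha=.05". It asks for a binomial test against 0.5 and a Wilson interval, with no EXACT statement and no continuity correction.

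The code serves the observed-case sensitivity analyses (modified FAS and PPS), the supportive analyses (modified FAS and FAS) and, through SAP 7.1.2, the same set for MAS Dynamic. SAP 7.4.1 gives the purpose of the observed-case method: "to assess the sensitivity of the MI and the LOCF method for primary and secondary effectiveness endpoints". The primary analysis uses multiple imputation and is not run with this code.

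**The concern.** Many statisticians take an unqualified binomial test to mean the exact one, yet the code shown gives the normal approximation. The two can disagree. With 60 responders among 100 subjects, the score test gives p = 0.0228 and the exact test gives p = 0.0284, so the same data fall on opposite sides of 0.025.

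The code is introduced only as similar to what will be run, so a programmer could add an exact test and still comply. The form of a pre-specified check would then be open to choice after the data are seen. Under the exact reading, the p-value could also contradict the Wilson interval reported beside it, and the visible text has no rule for that conflict.

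**Working it through.** **Inputs.** Null rate 0.50 (SAP 4); one-sided level 0.025 (SAP 7.1.1); 112 enrolled, up to 10% drop-out and at least 100 available for safety (Protocol 12.1). The assumed response rate is not legible. The pooled range of 90 to 112 is an assumption.

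**The plan's own figures.** 100/0.9 = 111.1, rounded up to 112, as stated. 1 − (1 − 0.016)^100 = 0.8007, against the stated 80%. The 90% power cannot be reproduced without the assumed rate.

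**Cut-offs at n = 100.** The score statistic is z = (k − n/2)/√(n/4).

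- k = 59: z = 9/5 = 1.80, p = 0.0359.
- k = 60: z = 10/5 = 2.00, p = 0.0228, so the score cut-off is 60.
- Exact tail: P(X ≥ 60) = 0.0284 and P(X ≥ 61) = 0.0176, so the exact cut-off is 61.

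**Cut-offs for n = 90 to 112.** They differ at 91, 93, 96, 98, 100, 102, 104, 105, 107, 109 and 111. That is 11 of 23 sizes, always by one responder. At n = 101 (61) and n = 112 (67) they coincide. For n = 100 to 112 the count is 7 of 13, so about half does not depend on the chosen range.

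**True one-sided size, P(X ≥ cut-off) at a rate of 0.5:**

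| Test | Minimum | Maximum | Mean over 23 sizes |
|---|---|---|---|
| Score (as coded) | 1.98% | 3.10% | 2.51% |
| Exact | 1.57% | 2.47% | 2.00% |

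**Agreement with the interval.** The Wilson interval inverts the score test, so its lower limit exceeds 0.5 exactly when the score p-value is below 0.025. A check of every count for n = 40 to 112 found no disagreement. For 60/100 the interval is 50.2% to 69.1%, in line with p = 0.0228.

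**Chance that the choice matters.** For each of the 11 sizes, take the probability that the count equals the score cut-off; sum these and divide by 23.

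| Assumed true rate | Average, n = 90 to 112 | At n = 100, P(X = 60) |
|---|---|---|
| 60% | 3.9% | 8.1% |
| 64% | 2.7% | 5.8% |
| 66.6% | 1.5% | 3.1% |
| 70% | 0.4% | 0.9% |

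The 66.6% row is the rate at which the exact test has 90% power at n = 100.

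**What an exact test would cost.** Power at n = 100, exact against score: 76.8% against 82.6% at a true rate of 64%; 87.7% against 91.4% at 66%; 97.9% against 98.8% at 70%.

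**Separate groups.** Protocol 12.1 states that "56 subjects need to be randomized to each treatment group". For groups of 50 to 56 the cut-offs differ at 50, 53 and 55. This range fits only the as-randomized FAS. Under SAP 7 the modified FAS uses realized groups, and subjects switching from A to B can move those outside it.

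**The case for a change.** The strongest case for a change is that a pre-specified check should not leave its test form open, since SAP 7.1 already fixes the interval type and the decimals of p-values. One sentence would close the gap. At the 11 sizes where the cut-offs differ, the score test's true size is 2.52% to 3.10%, above the stated 2.5%. Redaction is not an obvious explanation for the observed-case code, which is shown from its first line to its last.

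The arithmetic stands, and so does the observation that the visible text never names the form. Three things weaken the conclusion.

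- The code does answer the question. Only the word similar leaves room, and the coded form is the one that matches the pre-specified Wilson interval.
- The visible text attaches no success criterion to an observed-case p-value. These analyses are labelled sensitivity or exploratory, and Protocol 12.4.4.4 treats the separate group tests as exploratory. The comparison with the imputed result rests on estimates and intervals, which are the same under either test.
- The silence may not be complete. SAP 7.1.1 refers to code given above where none is visible, and SAP 4 and 7.1 have redactions beside their descriptions of the test.

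The count of 11 in 23 also overstates the effect: it counts sample sizes, not the chance of a different result.

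**Conclusion.** No change is needed. This is a detail that the SAP's own code fills sensibly. Run as written, the observed-case analyses use the asymptotic score test with 2.5% as a nominal level. Over the assumed range its true size averages 2.51%, and it never conflicts with the reported interval. Moving to an exact test would be a fair alternative, but it exchanges power for strict size control (87.7% against 91.4% at n = 100 and an assumed rate of 66%) and corrects no error.

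The difference is at most one responder. It alters a conclusion in about 0.4% to 2.7% of trials at assumed true rates of 70% down to 64%, or 3.9% at 60%, averaged over an assumed pooled n of 90 to 112. It is confined to sensitivity and supportive analyses. Nothing here bears on the imputed primary test, whose combining details are not visible. An author revising the SAP for other reasons could name the score test in passing, but no result would change.

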7.1.2 Secondary Effectiveness Endpoints

MAS ratings

One secondary effectiveness endpoint is the proportion of responders (response rate) defined as subjects with \geq 1-point improvement on the MAS 'Décolleté Wrinkles – Dynamic' from baseline to 16 weeks after last treatment as assessed [REDACTED]. Same analyses as for the primary endpoint will be performed on this endpoint (including sensitivity and supportive exploratory analyses on the same analysis sets and treatment groups).

Satisfaction with décolleté appearance

[figure not shown]
Number and percentage (n, %) of subjects with treatment satisfaction defined by a level of 1, 2 or 3 will be summarized and the corresponding two-sided 95% confidence intervals will be provided for the pooled treatment groups (overall).

[figure not shown]
GAIS

[figure not shown]
Number and percentage (n, %) of subjects with "improvement" in iGAIS-Wrinkles defined as a rating of 1, 2 or 3 at 16 weeks after last treatment will be summarized and two-sided 95% confidence intervals will be provided for the pooled treatment groups. Analogous methods will be used for sGAIS-Wrinkles.

7.2 Safety Endpoints

All safety analyses will be performed on the SES.

AEs will be coded according to the Medical Dictionary for Regulatory Activities (MedDRA) version in effect at the time the database is closed. Only TEAEs will be analyzed, which are defined as AEs with onset or worsening at or after date of first injection of the IMD. Incidences will be calculated for TEAEs on the system organ class (SOC) level and on the preferred term (PT) level (i.e., total and percentage, by intensity, and by relationship). Listings and (as

applicable) tables displaying incidences for TEAEs leading to discontinuation, serious TEAEs, and deaths will also be provided.

Each documented worsening of an AE will be aggregated with the previous corresponding AE record. The start date of the AE will be the date of the record reporting the onset of the AE with the first reported intensity and the stop date will be the last stop date of all aggregated worsening records or considered ongoing, if not yet resolved. For intensity, the worst attribute will be chosen.

CAVE: there is one exception, where an aggregation of the AE with corresponding worsening(s) is not allowed: if the AE record started before the first treatment and the worsening record started (worsened) at or after date of first treatment. In that case, only the AE record(s) starting at or after treatment will be aggregated and regarded as TEAE (see also below).

[figure not shown]
In case of missing intensity or missing causal relationship of an AE the worst case principle will be applied, i.e. a missing intensity will be set to “severe” and a missing causal relationship will be set to “related”. Missing data of the worst outcome will be imputed by “unknown”.

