6.2 Discussion of Investigational Design, Including Choice of Control Groups

The prospective, parallel-group, randomized, multicenter investigational design was chosen to adequately investigate the effectiveness and safety of the IMD.

In general, prospective designs can achieve a higher data quality compared to retrospective designs because they usually have fewer potential sources of bias and confounding than retrospective studies. A disadvantage of prospective studies is the risk of bias such as the loss of individuals to follow up during the investigation.

Up to 10 sites were chosen to improve data homogenization and to minimize siteassociated biases. Using several investigation sites increases the representativeness of the investigational results and decreases investigation site-related biases.

All the do not know which treatment protocol was applied (either 2 or 3 injection cycles) which helps minimize bias due to demand characteristics (what the evaluator expects). As this investigation has no control group, the subject and the treating investigator cannot be blinded.

A parallel-group design was chosen to evaluate two different treatment algorithms at once. Randomization eliminates bias in treatment assignment, specifically selection bias and confounding.

The general duration of 52 weeks will also allow assessing the late-onset reactions [Bass 2010, Smith 2007].

The injection technique approach follows the consensus guidelines mentioned above: the IMD has to be placed in th

Rationale

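### Merging AE worsenings across later injections can leave later cycles undercounted in the by-cycle table of related TEAEs

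*SAP*

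**What the plan says.** SAP 7.2 (Safety Endpoints) sets the derivation rule: "Each documented worsening of an AE will be aggregated with the previous corresponding AE record". On timing it says: "The start date of the AE will be the date of the record reporting the onset of the AE with the first reported intensity". On severity it says: "For intensity, the worst attribute will be chosen". It then limits the rule: "there is one exception, where an aggregation of the AE with corresponding worsening(s) is not allowed". That exception applies "if the AE record started before the first treatment and the worsening record started (worsened) at or after date of first treatment". Later injections are not mentioned.

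SAP 7.4.5 (Examination of Subgroups) plans safety tables for the "subgroup of subjects that had three injections with a cannula". Among them: "Treatment-related TEAEs will be presented by injection cycle". Protocol 6.2 describes the two regimens as "either 2 or 3 injection cycles".

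Protocol 10.1.2 lists the date of worsening among the items recorded for each AE. Parts of SAP 7.2, 7.2.2 and 7.4.5 are not shown in the public version.

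**The concern.** The stated exception treats a worsening after first exposure as emergent to that exposure. The same reasoning applies to injections 2 and 3, but the rule does not extend to them. A reaction that begins after injection 1, persists, and worsens after injection 2 therefore becomes one record dated to cycle 1. One record with one start date cannot show the reaction in both cycles.

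The regimens differ in the number of injections, and Protocol 4.2 says the study should help to determine the appropriate regimen. The by-cycle table is the visible output that bears most directly on what a further injection adds. If cycle is taken from the merged start date, the loss of event counts runs one way, out of later cycles.

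The documents make such events plausible. Treatment lasts about 4 months (Protocol 8.2.4). Over-correction is to be recorded as an AE and is described as resolving over six to 12 months (Protocol 8.2.6), so one that arises at injection 1 could still be present at later injections.

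**Working it through.** **The plan's own safety figure.** SAP section 4 gives an 80% probability of seeing at least one AE with true probability 1.6% among 100 subjects. Check: 1 − (1 − 0.016)^100 = 1 − 0.984^100 = 0.8007. The figure reproduces and is not in dispute. It concerns overall detection, not assignment to a cycle.

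**The rule applied to one event.** The injection dates are not visible, so days 1, 57 and 113 are assumed (day 113 fits a treatment period of about 4 months). Suppose a related reaction is mild from day 3 and worsens to severe on day 60 without resolving.

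| Handling | Cycle 1 (days 1–56) | Cycle 2 (days 57–112) |
|---|---|---|
| Records kept separate | one entry, mild | one entry, severe |
| SAP 7.2 merge, cycle taken from start date | one entry (start day 3; merged intensity severe) | no entry |

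The cycle 1 entry is correct as an event under both. What is lost is the cycle 2 entry. The exception does not apply, because the onset on day 3 is after the first treatment.

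**Which steps are stated and which are inferred.**
1. A worsening is merged with the earlier record: stated.
2. The merged event has the first start date: stated.
3. The only exception concerns the first treatment: stated.
4. The by-cycle table uses merged records and assigns cycle by start date: inferred. It is the natural reading, but no rule is visible.

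**Possible size.** The documents give neither the subgroup size N nor the proportion w with a related AE that is ongoing at a later injection and worsens after it. Assume N = 20 to 50 and w = 1% to 10%. The upper N is close to one randomized group of 56 after the planned 10% loss: 56 × 0.9 = 50.4. The expected number of subjects missing an entry is N × w, and the probability of at least one is 1 − (1 − w)^N.

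| N | w | Expected | P(at least one) |
|---|---|---|---|
| 20 | 1% | 0.2 | 18.2% |
| 20 | 10% | 2.0 | 87.8% |
| 40 | 5% | 2.0 | 87.1% |
| 50 | 1% | 0.5 | 39.5% |
| 50 | 10% | 5.0 | 99.5% |

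**Overall incidence.** A subject with such an event counts once for that preferred term whether or not the records are merged. The secondary safety endpoint (related TEAEs by SOC and PT) is therefore unchanged when the merged records carry the same causality.

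**The case against.** The strongest reply is that SAP 7.2 governs when records are merged, not how a merged event is placed in a cycle. A cycle rule may exist in text that is not shown, and such a gap is not an omission from the plan. This stands, and it is why the conclusion is conditional. It does not remove the point: the visible text allows only one exception to merging, and a single dated record cannot appear in two cycles.

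Other points that stand:
- The visible by-cycle table covers only subjects with three cannula injections, and per-injection burden is not a stated objective or endpoint.
- Few events qualify. The AE must be ongoing at the next injection and recorded as a worsening. The protocol expects reactions to be mostly transient, and a reaction that resolved and recurred would presumably be a new AE.
- Nothing is lost from the data. Worsening dates are collected and all eCRF data are listed.
- Counting one continuous AE in two cycles is also a convention, and its cycle counts need not sum to the number of AEs.

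A reader might infer more than the documents support:
- *Severity is shifted into earlier cycles, so the first injection looks worse.* No table of intensity by cycle is visible, and the cycle 1 onset did occur in cycle 1, so its count is not inflated.
- *Later cycles can only lose.* This holds for event counts under start-date assignment. If intensity were shown by cycle, cycle 2 could take on an intensity first reached after injection 3.
- *The protocol synopsis requires the worst causality when records are merged.* It asks for incidences to be tabulated by worst causal relationship; it sets no merging rule.

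**Conclusion.** The point holds in a limited, conditional form. As written, SAP 7.2 merges a worsening across injections 2 and 3. If the SAP 7.4.5 table is built from the merged records by start date, a related AE that is ongoing at a later injection and worsens afterwards is missing from the later cycle, and later cycles can be undercounted.

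The number affected is unknown and probably small. The range of 0.2 to 5 subjects rests entirely on the assumed subgroup size and proportion. The secondary safety endpoint is not affected, provided the merged records agree on causality. This is a cheap improvement to one subgroup table; it does not show that the safety analysis as a whole is biased.

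**What to change.** Keep the merged records for overall incidence. Add to SAP 7.2 or 7.4.5, for by-cycle tables only:
- A worsening dated on or after a later injection is not merged across that injection.
- It is counted in the cycle in which the worsening began, with its own intensity and causality.
- The rule for assigning an AE to a cycle is stated explicitly. If text not shown already contains one, the two should be aligned.
- A footnote says that one AE may appear in more than one cycle, so cycle counts may exceed the total number of AEs.

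The cost is a few SAP sentences and minor programming. No new data are needed, because the date of worsening is already in the eCRF. The one downside is that cycle counts may no longer add up to the total, which the footnote covers.
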